7.9.3 Powered Secondary Endpoints

There are five hypothesis-tested secondary endpoints defined for the trial. Type I error will be controlled by a serial gatekeeping procedure according to the details in **Section 7.5**. Hypothesis testing of the secondary endpoints will only occur if both the clinical outcome composite and valve function composite endpoints are met.

7.9.3.1 Powered Secondary Objective #1: BVD in Female Population

The first powered secondary endpoint in this trial is the BVD rate at 12 months post-procedure within the female population. The endpoint will be analyzed as described for the Valve Function Composite Endpoint in **Section 7.9.2** in female subjects using the Implanted analysis set. Superiority of the Medtronic SE TAV to Edwards BE TAV in BVD for females will be declared if the one-sided p-value for the difference (SE TAV – BE TAV) is less than or equal to 0.025.

7.9.3.2 Powered Secondary Objective #2: HSVD

The second powered secondary endpoint is the HSVD rate at 12 months post-procedure. HSVD is defined as having mean aortic gradient ≥ 20mmHg and will be reported according to data collected on the core lab TTE CRF at 12 months. The endpoint is designed to evaluate if Medtronic SE TAV is superior to Edwards BE TAV in HSVD at 12 months post-procedure. Formally, the hypothesis is as follows:

 $H_o: \pi_{\mathsf{MDT}} \geq \pi_{\mathsf{EW}}$

 $H_A: \pi_{\mathsf{MDT}} < \pi_{\mathsf{EW}}$

In the above expression π_{MDT} and π_{EW} denote the HSVD rates at 12 months post-procedure for Medtronic SE TAV and Edwards BE TAV, respectively.

The endpoint will be analyzed as described for the Valve Function Composite Endpoint in **Section 7.9.2** using Kaplan-Meier analysis. Superiority of the Medtronic SE TAV to Edwards BE TAV in HSVD will be declared if the one-sided p-value for the difference (SE TAV – BE TAV) is less than or equal to 0.025. The analysis will be performed using the Implanted analysis set.

7.9.3.3 Powered Secondary Objective #3: Hemodynamic Mean Gradient

The third powered secondary endpoint in this trial is the hemodynamic mean gradient as continuous variable at 12 months post-procedure. The endpoint is designed to show the Medtronic SE TAV is superior to Edwards BE TAV in hemodynamic mean gradient at 12 months post-procedure. Formally, the hypothesis is as follows:

 $H_o: MGV_{MDT} \ge MGV_{EW}$

H_A: MGV_{MDT} < MGV_{EW}

In the above expression MGV_{MDT} and MGV_{EW} denote the hemodynamic mean gradient (MGV) as continuous variable at 12 months post-procedure for Medtronic SE TAV and Edwards BE TAV, respectively.

Within treatment arm, the MGV at 12 months will be summarized descriptively. Superiority of the endpoint will be evaluated using analysis of covariance (ANCOVA) with baseline MGV as a covariate. Along with the descriptive summary statistics of MGV at 12 months within treatment arm, the

SMART Trial Statistical Analysis Plan	Form
Revision 5.0 Page 20 of 27	Medtronic

difference (SE TAV – BE TAV) in least square means (LS-means) with corresponding upper limit from the two-sided 95% confidence interval, and one-sided p-value from the ANCOVA will be presented. If the one-sided p-value is less than or equal to 0.025, superiority of the Medtronic SE TAV compared to Edwards BE TAV will be met. The analysis will be performed using the Implanted analysis set and will include subjects with available MGV at 12 months from the core lab.

7.9.3.4 Powered Secondary Objective #4: Effective Orifice Area

The fourth powered secondary endpoint in this trial is the effective orifice area as continuous variable at 12 months post-procedure. The endpoint is designed to show the Medtronic SE TAV is superior to Edwards BE TAV in EOA at 12 months post-procedure. Formally, the hypothesis is as follows:

 $H_0: EOA_{MDT} \leq EOA_{EW}$

 $H_A: EOA_{MDT} > EOA_{EW}$

In the above expression EOA_{MDT} and EOA_{EW} denote the effective orifice area (EOA) as continuous variable at 12 months post-procedure for Medtronic SE TAV and Edwards BE TAV, respectively.

Within treatment arm, the EOA at 12 months will be summarized descriptively. Superiority of the endpoint will be evaluated using ANCOVA with baseline EOA as a covariate. Along with the descriptive summary statistics of EOA at 12 months within treatment arm, the difference (SE TAV – BE TAV) in LSmeans with corresponding lower limit from the two-sided 95% confidence interval, and one-sided pvalue from the ANCOVA will be presented. If the one-sided p-value is less than or equal to 0.025, superiority of the Medtronic SE TAV compared to Edwards BE TAV will be met. The analysis will be performed using the Implanted analysis set and will include subjects with available EOA at 12 months from the core lab.

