9.3 Inclusion Criteria

Prospective subjects must meet ALL of the following inclusion criteria to be eligible for participation:

- Symptomatic subjects with predicted risk of operative mortality < 15% at 30-days per multidisciplinary local heart team assessment
- 12. Severe aortic stenosis, defined as: Aortic valve area ≤1.0 cm² (or aortic valve area index of ≤0.6 cm²/m²), OR mean gradient ≥40 mmHg, OR maximal aortic valve velocity ≥4.0 m/sec by transthoracic echocardiography at rest
- 13. Aortic valve annulus area ≤ 430 mm² based on MDCT
- 14. Subject's anatomy is appropriate for both Medtronic and Edwards TAV Systems used within the conduct of the trial
- 15. Subject's anatomy is suitable for TAVR via transfemoral vessel access
- 16. Commercial indication for transcatheter aortic valve replacement (TAVR), in conformity with both local regulations and Instructions for Use (IFU)
- 17. Subject and the treating physician agree that the subject will return for all required post-procedure follow-up visits

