18.4 Appendix IV: MDCT Procedures: Pre-TAVR Planning

MDCT is required to confirm anatomical suitability for transfemoral TAVR with the Evolut PRO/PRO+/FX and SAPIEN 3/3 Ultra Systems. MDCT is used to evaluate aortic valve anatomy, determine aortic root dimensions for device sizing, and to evaluate peripheral vessel dimensions and anatomy. The MDCT exam should be performed at the trial center, but exams performed for diagnostic purposes outside the trial center and prior to consent can be used, provided they are within 365 days prior to submission for Confirmation of Qualification and contain the protocol-required data.

Technical Aspects. Technical aspects of the exam are per the site's standard routine for clinical TAVR cases; however, the following are recommended parameters:

- Detector collimation 0.4-0.625 mm.
- Slice thickness ≤ 1.0 mm.
- Coverage area from superior to the aortic arch to inferior to the cardiac apex.
- Slice overlap of 0.4 mm (will result in isotropic voxels with a 20 cm field of view)

Required Variables. The following variables should be captured to confirm anatomical suitability for implantation and TAV size selection (**Figure 15**).

- Annulus area (measured at systole and diastole)
- Annulus perimeter (measured at systole if retrospective gating is used)
- Sinus of Valsalva (SoV) diameters (measured at diastole)
 - o Right coronary sinus diameter
 - Left coronary sinus diameter
 - Non coronary sinus diameter
 - Mean sinus diameter (mean of the three coronary sinus diameters)
- SoV heights (measured at diastole)
 - o Right coronary SoV height
 - Left coronary SoV height
 - Non coronary SoV height
 - Mean SoV height (mean of the three SoV heights)
- Mean diameter of left iliofemoral artery
- Mean diameter of right iliofemoral artery

These variables should be documented in the MDCT report for the subject's medical record or on an alternative source document to be maintained in the subject's trial files (e.g. a report from dedicated off-line cardiac image analysis system such as 3mensio, Vital Images, etc.).

Version 4.0, 15-Dec-2021

Page 100 of 131

Medtronic

[figure not shown]

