7.4 Handling of Missing, Unused, and Spurious Data and Dropouts

Every effort will be undertaken to minimize missing data. In time-to-event outcomes, dropouts will be censored at the time of discontinuation, consistent with the Kaplan-Meier approach. Unless otherwise specified, no statistical techniques will be used to impute missing data. The number of subjects included in each analysis will be reported so that the reader can assess the potential impact of missing data. To evaluate the potential impact of missing data on study results, sensitivity analyses will be performed for the primary endpoints which will include a tipping point analysis.

In the case of partial dates, if only the month and year are known, the event or assessment will be analyzed as if it occurred on the 15th of that month. If only the year is known, the event or assessment will be analyzed as if it occurred on June 30th of that year. Imputation of partial dates is subject to the restriction that pre-implant events must occur between the date of informed consent and the date of implant and post-implant events must occur after the date of implant and prior to date of study exit.

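### The ANCOVAs for 12-month mean gradient and EOA lose subjects with no baseline value and leave out sex and MDCT annulus area

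*SAP*

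**What the plan says.** **Model.** For EOA, SAP 7.9.3.4: "Superiority of the endpoint will be evaluated using ANCOVA with baseline EOA as a covariate". For mean gradient (MGV), SAP 7.9.3.3: "Superiority of the endpoint will be evaluated using analysis of covariance (ANCOVA) with baseline MGV as a covariate". No other covariate is named in either section.

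**Who is analysed.** Within the Implanted set, the EOA analysis "will include subjects with available EOA at 12 months from the core lab" and the gradient analysis "will include subjects with available MGV at 12 months from the core lab". Neither section says what happens when the baseline value is missing.

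**Missing data.** SAP 7.4 sets a default: unless a section specifies otherwise, "no statistical techniques will be used to impute missing data". Neither 7.9.3.3 nor 7.9.3.4 specifies otherwise. The carry-forward rules for BSA and BMI serve PPM only, and the sensitivity analyses for missing data cover the primary endpoints only.

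**What the baseline value is.** Exclusion criterion E10 rules out earlier aortic valve replacement, so the baseline measurement is of the native valve. Protocol 18.3.4 calls that area AVA and reserves EOA for the prosthesis.

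**What else is on file.** Randomisation is stratified by site and sex (Protocol 10.1.1, SAP 5). Annulus area is needed for I3, and the required MDCT variables in Protocol 18.4 begin with "Annulus area (measured at systole and diastole". Sex is used only in separate by-sex analyses (SAP 7.9.5).

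**The concern.** An ANCOVA needs a covariate value for every subject it analyses. With no imputation, the model keeps only subjects who have both a baseline and a 12-month value, whereas the SAP describes a set defined by the 12-month value alone. The two statements agree only if no baseline value is missing.

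The one covariate chosen is a measurement of a valve that the procedure takes out of function. It may or may not predict how the prosthesis performs; the documents do not say. Two variables that should be known for essentially every subject before implant, sex and annulus area, are not used.

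At stake are the width of the confidence intervals for the two treatment differences and a clear statement of who contributes to them. SAP 7.5 tests these endpoints first (MGV) and second (EOA) in the secondary sequence.

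**Working it through.** **1. Reproduce the plan's sample sizes.** Inputs from SAP 6: EOA 2.27 ± 0.65 versus 1.72 ± 0.37 cm² (difference 0.55); MGV 9.0 ± 3.3 versus 13.7 ± 5.6 mmHg (difference 4.7); one-sided alpha 0.025; 80% power; unequal-variance t-test.

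- EOA: noncentrality at n = 16 per arm is 0.55 / √((0.65² + 0.37²)/16) = 2.94, giving 80.5% power. The stated 16 per arm is reproduced.
- MGV: 17 per arm suffices (81.8%). The stated 20 gives 87.9%, so it is conservative.

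**2. Power after losing subjects.** Start from 350 per arm (700 as-treated, 1:1), and let m be the share with no baseline value. The documents do not give m, so it is assumed. Take no gain from the covariate. The root-mean-square SDs are √((0.65² + 0.37²)/2) = 0.529 cm² and √((3.3² + 5.6²)/2) = 4.596 mmHg. The 95% half-width is 1.96 × SD × √(2/n).

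| m (assumed) | n per arm | EOA half-width, cm² | MGV half-width, mmHg | Power, both |
|---|---|---|---|---|
| 0 | 350 | 0.078 | 0.68 | >99.9% |
| 10% | 315 | 0.083 | 0.72 | >99.9% |
| 20% | 280 | 0.088 | 0.76 | >99.9% |
| 30% | 245 | 0.094 | 0.81 | >99.9% |

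Power stays at or above 99% down to 36 per arm (EOA) and 37 per arm (MGV).

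**3. When does adjusting for baseline pay?** Let R² be the share of outcome variance that the baseline value explains. Compared with an unadjusted analysis of everyone with a 12-month value, the interval width changes by √((1 − R²)/(1 − m)), taking missingness as unrelated to outcome.

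| m | R² = 0 | 0.05 | 0.10 | 0.20 |
|---|---|---|---|---|
| 5% | 1.026 | 1.000 | 0.973 | 0.918 |
| 10% | 1.054 | 1.027 | 1.000 | 0.943 |
| 20% | 1.118 | 1.090 | 1.061 | 1.000 |

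The break-even is R² = m, that is a correlation of 0.22, 0.32 or 0.45 at 5%, 10% or 20% missing. The sign therefore depends on two quantities that the documents do not give.

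**4. Filling instead of dropping.** Setting a missing baseline to the pooled mean keeps every subject, and the covariate then explains (1 − m)R². The width factor is √(1 − (1 − m)R²), which is never above 1 apart from one degree of freedom. At m = 10% and R² = 0.10 it is √(1 − 0.09) = 0.954, against 1.000 when subjects are dropped. Filling is at least as precise as dropping whenever R² ≤ 1/(2 − m), which is 0.526 at m = 10%.

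**5. Adding sex and annulus area.** If together they explained 5% to 30% of the outcome variance (assumed), the width factor would be √0.95 = 0.975 to √0.70 = 0.837, so 2.5% to 16% narrower. If they explained nothing, the cost would be two degrees of freedom.

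**The case against.** The strongest reply is that no conclusion turns on this. Power is above 99.9% across any plausible loss. An 8% wider EOA interval would be about 0.08 × 0.078 = 0.006 cm², against a planned difference of 0.55. ANCOVA on the baseline value is a valid prespecified analysis. Leaving out a stratification factor costs precision and makes the test slightly conservative, but does not invalidate it. SAP 7.4 also commits to reporting the number analysed, so any loss would be visible. All of that stands.

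Several stronger readings are tempting, and the documents do not support them:

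- *That the SAP forbids imputation.* Section 7.4 is a default that other sections may override. The gap is that 7.9.3.3 and 7.9.3.4 do not.
- *That I2 shows baseline areas will be missing.* I2 does accept severe stenosis by area, "OR mean gradient ≥40 mmHg, OR maximal aortic valve velocity ≥4.0 m/sec", but it sets eligibility thresholds, not which variables are measured. Protocol 18.3.2 and 18.3.4 ask for every input to valve area, and for the mean gradient.
- *That the baseline covariate costs more than it returns.* Step 3 shows that either sign is possible.
- *That annulus area determines valve size in both arms.* The tables in Protocol 18.4.1 use area for SAPIEN, but perimeter and mean diameter for Evolut. The 430 mm² ceiling may also weaken its correlation with outcome.
- *That baseline EOA is a substantive error.* The formulas differ only in native versus prosthetic VTI, so this is a label to correct.

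Site is the other stratum and is also absent. With about 700 subjects at about 90 sites, roughly 8 per site, its absence is not pressed here.

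**Conclusion.** The point holds as a modest improvement. The stated inclusion rule and the fitted model disagree for any subject without a baseline value, and two covariates already collected are left unused.

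A reader might infer a risk to the secondary testing sequence because these endpoints come first in it. The documents do not support that: at the planned differences the tests are not in danger. That rests on the planned differences. At half of them, power is still 99.99% with 245 per arm. At a quarter, a 30% loss would lower power from about 93% to 82% (EOA) and from about 92% to 81% (MGV).

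Nor is bias to be inferred. The screening echo precedes randomisation, so its absence should not depend on arm. The fallback echo in Protocol 10.1.2 precedes implant, and nothing in the documents suggests that its completion differs by arm.

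The effect is on precision and on the definition of the analysed set. Its size cannot be stated, because the missing rate and the correlations are not given; the ranges in the working are assumptions.

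**What to change.** In SAP 7.9.3.3 and 7.9.3.4:

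- Fit 12-month MGV and 12-month EOA each on treatment, sex, MDCT annulus area and the core-lab baseline echo value.
- Name one phase for annulus area in advance, for example the systolic measurement, because both phases are recorded.
- Call the EOA baseline covariate native AVA, and state which pre-implant echo supplies it.
- Set a missing baseline value to the mean over both arms, and record this as an exception to 7.4. The rule uses neither outcome nor arm, and every implanted subject with a 12-month core-lab value is then analysed, as the SAP already says.

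The cost is SAP wording and a small programming change. All the data are already collected, and the hypotheses, alpha and testing order do not change.

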7.9.3.5 Powered Secondary Objective #5: Moderate or Severe Prosthesis-Patient Mismatch

The fifth powered secondary endpoint is the rate of moderate or severe PPM at 30 days post-procedure. PPM is defined for the valve function composite endpoint in Section 7.9.2 and will be reported according to data collected on the core lab TTE CRF at 30 days. The endpoint is designed to evaluate if Medtronic SE TAV is superior to Edwards BE TAV in moderate or severe PPM at 30 days post-procedure. Formally, the hypothesis is as follows:

 $H_o: \pi_{MDT} \geq \pi_{EW}$

 H_A : $\pi_{MDT} < \pi_{EW}$

In the above expression π_{MDT} and π_{EW} denote the rate of moderate or severe PPM at 30 days postprocedure for Medtronic SE TAV and Edwards BE TAV, respectively.

Moderate or severe PPM will be defined as follows:

For subjects with BMI < 30 kg/m^2

- **Moderate PPM:** EOAI = $0.85 0.65 \text{ cm}^2/\text{m}^2$
- Severe PPM: EOAI = $\leq 0.65 \text{ cm}^2/\text{m}^2$

Rev C

Medtronic

Page 21 of 27

For subjects with BMI \geq 30 kg/m²

- **Moderate PPM:** EOAI = $0.70 0.55 \text{ cm}^2/\text{m}^2$ •
- Severe PPM: EOAI = $\leq 0.55 \text{ cm}^2/\text{m}^2$ •

where EOAI = EOA / BSA (body surface area).

Superiority of the endpoint will be evaluated using the absolute risk difference (SE TAV – BE TAV) in the rate of moderate or severe PPM at 30 days. The endpoint will be reported with the PPM rate within treatment arm, the absolute risk difference in the rate of moderate or severe PPM (SE TAV – BE TAV) with corresponding upper limit from the two-sided 95% Wald confidence interval, and the one-sided pvalue for the superiority hypothesis. If the one-sided p-value is less than or equal to 0.025, the endpoint will be considered met. Within each arm, the numerator will include the number of subjects with moderate or severe PPM based on the core lab at 30 days and the denominator will include all subjects evaluable for PPM (i.e., have evaluable BMI and EOAI at 30 days to be defined as a known success or failure). If BSA and BMI are missing at the 30-day echo, last observation carried forward method will be used in which the latest available BSA or BMI between baseline and the 30-day echo will be used. The analysis will be performed using the Implanted analysis set.

7.9.4 Non-Powered Secondary Objectives

Additional outcome measures are defined for the trial without pre-specified hypothesis testing planned and all analyses will be descriptive and will reported by treatment arm.

1. Device success at 30 days

Device Success is defined as meeting all of the following:

- Freedom from mortality AND
- Correct positioning of a single prosthetic heart valve into the proper anatomical location • AND
- Intended performance of the prosthetic heart valve (no prosthesis-patient mismatch (PPM) and mean aortic valve gradient <20 mmHg or peak velocity <3 m/s) AND No moderate or severe prosthetic valve regurgitation)

Components of device success will be reported on the procedure CRF, the echo core lab CRF at 30 days (or discharge when the 30-day echo is not available), and CEC CRF:

- Mortality will be defined as any death occurring within 30 days of implant or prior to • hospital discharge.
- Correct positioning of the single prosthetic heart valve into the proper anatomical • location will be reported by the investigator on the procedure CRF.
- Absence of PPM will be derived from the echo core lab data at 30 days. If the 30-day echo is not available, the discharge echo will be used. If BSA and BMI are missing at the visit, last observation carried forward method will be used in which the latest available BSA or BMI between baseline and the echo used for device success will be used. PPM is

SMART Trial Statistical Analysis Plan Form Revision 5.0 Page 22 of 27 Medtronic

defined in **Section 7.9.3.5**. Subjects with available BMI and EOAI will have known PPM and be included in the analysis of the component.

- Mean aortic valve gradient < 20 mmHg (or peak velocity < 3 m/sec) will be derived from the echo core lab CRF at 30 days or discharge when the 30-day echo is unavailable.
- Absence of moderate or severe prosthetic valve regurgitation will be derived from the echo core lab CRF at 30 days or discharge when the 30-day echo is unavailable.

The endpoint will be reported within treatment arm as the count and percentage of subjects achieving device success with two-sided 95% exact binomial confidence interval. Subjects will be defined as success if all components are met. Subjects will be defined as failure if any one component with available data is not met, regardless of if data are available for all components. Subjects missing data for any components and not meeting criteria for failure will be considered to have a missing outcome. The numerator will include the number of subjects with device success and the denominator will include subjects evaluable for device success (known status of success or failure). The components of device success will also be summarized descriptively. The endpoint will be analyzed using the AT analysis set for all subjects where the delivery catheter was introduced.

2. Incidence of an early safety composite at 30 days defined as:

- All-cause mortality
- All stroke (disabling and non-disabling)
- Life-threatening bleeding
- Acute kidney injury—Stage 2 or 3 (including renal replacement therapy)
- Coronary artery obstruction requiring intervention
- Major vascular complication
- Valve-related dysfunction requiring repeat procedure (BAV, TAVR, or SAVR)

Components of the early safety composite will be adjudicated by the CEC and analysis will be based on the data collected on the CEC adjudication form. The overall composite will be based on occurrence of the earliest component event and only events within 30 days will be considered for the analysis. The rate at 30 days will be estimated by Kaplan-Meier survival analysis. The rate at 30 days for each component will also be reported. Analysis of the endpoint will use the AT analysis set.

3. Hospital readmission for any cause at 30 days

Hospital readmission will be based on data collected on the site-reported rehospitalization form. The rate at 30 days will be estimated by Kaplan-Meier survival analysis. Analysis of the endpoint will use the AT analysis set.

4. Incidence of clinical efficacy (after 30 days) at 12 months and annually to 5 years defined as a composite of:

- All-cause mortality
- All stroke (disabling and non-disabling)
- Requiring hospitalizations for valve-related symptoms or worsening congestive heart failure

Form

- NYHA class III or IV •
- Valve-related dysfunction (mean aortic valve gradient \geq 20 mmHg, EOA \leq 0.9-1.1 cm² and/or DVI <0.35m/s, AND/OR moderate or severe prosthetic valve regurgitation)

Page 23 of 27

Note that the EOA threshold of 0.9 applies for subjects with BSA <1.6 m² and EOA threshold of 1.1 applies for subjects with BSA \geq 1.6 m². The endpoint will be evaluated at each time point using the point estimates from a Kaplan-Meier analysis. Components of the endpoint will be reported on the echo core lab CRF, the follow-up visit CRF, and the CEC CRF. Events occurring within 12 months and annually to 5 years, will be counted towards the event rate at each time point. Time to event for the overall composite will be based on the earliest component event; components of the event (NYHA class, valve-related dysfunction) that are detected on scheduled follow-up visits (e.g., 12 months) will be the minimum of the assessment date or the visit target date (e.g., 365 days). Censoring time will be the last available time where subjects are known to be fully event free. Subjects with an event within 30 days will be excluded from the analysis. Analysis of the endpoint will use the Implanted analysis set.

5. Components of the primary clinical endpoint at 12 months and annually to 5 years:

- Mortality •
- **Disabling stroke** •
- Heart failure rehospitalization

Mortality, disabling stroke, and heart failure rehospitalization will be adjudicated by the CEC and analysis will be based on data collected on the CEC adjudication form. Each component will be analyzed with Kaplan-Meier survival analysis according to Section 7.2 for each time point. Analysis of the endpoint will use the AT analysis set.

6. New pacemaker implantation rate at 30 days, 12 months and annually to 5 years

New pacemaker implantation will be reported according to data reported by the investigator on the Permanent Pacemaker Implant CRF. The endpoint will be analyzed with Kaplan-Meier survival analysis according to Section 7.2 for each time point. Analysis of the endpoint will use the AT analysis set, excluding patients with PPI or ICD prior to the study TAVR procedure.

7. Aortic valve re-intervention at 30 days, 12 months and annually to 5 years

Aortic valve re-intervention will be adjudicated by the CEC and analysis will be based on data collected on the CEC adjudication form. The endpoint will be analyzed with Kaplan-Meier survival analysis according to Section 7.2 for each time point. Analysis of the endpoint will use the AT analysis set.

8. 6MWT at 30 days, 12 months and annually to 5 years

The six-minute walk test (6MWT) measures the distance walked in meters (m). Distance walked at each time point will be summarized as a continuous outcome within treatment arm. The number of subjects unable to perform the test will also be tabulated by reason at each visit. Within each arm, change from baseline will be summarized descriptively. Analysis will be performed using the AT analysis set for all subjects able to complete the assessment at the follow-up visit.

9. QoL (KCCQ, EQ-5D) at 30 days, 12 months and annually to 5 years

056-F286, Statistical Analysis Plan Template

Medtronic

Revision 5.0

The Kansas City Cardiomyopathy Questionnaire (KCCQ) is a 23-item self-administered instrument and responses will be collected in the CRF. The domain and summary scores include: Physical Limitation, Symptom Stability, Symptom Frequency, Symptom Burden, Total Symptom Score, Self-efficacy, Quality of Life, Social Limitation, Overall Summary Score, and Clinical Summary Score. At each follow-up time point, the overall summary score and clinical summary score will be summarized descriptively as continuous data within treatment arm. For each treatment arm, change from baseline will be summarized. Analysis will be performed using the AT analysis set.

The EQ-5D Index will be summarized as continuous data within treatment arm at each follow-up timepoint. Additionally, for each treatment arm, change from baseline will be summarized descriptively. Analysis will be performed using the AT analysis set.

10. BVD (HSVD, NSVD, thrombosis, endocarditis, and aortic valve re-intervention) at 2 to 5 years annually

The endpoint will be derived following the same principles as described for the valve function composite co-primary endpoint in **Section 7.9.2**, with same method used for the primary analysis at 12 months. Cutoff days for point estimates are 730, 1095, 1465, and 1825 for analysis time points of 2 years, 3 years, 4 years, and 5 years, respectively. Time to event for events detected on scheduled follow-up echos at 2 years, 3 years, 4 years, and 5 years will be the minimum of the echo date or the visit target date (e.g., 365 days). As in the primary endpoint analysis, HSVD and NSVD events detected through the maximum of the annual visit echo date or the end of the corresponding visit window will be counted to ensure inclusion of events detected on unscheduled echos. Thrombosis, endocarditis, and aortic valve re-intervention events detected through the visit target date (730, 1095, 1465, and 1825 days respectively) will be counted. Components of the endpoint will also be reported at each time point. Analysis will use the Implanted analysis set.

Given the increasing impact of mortality on availability of the BVD endpoint at later time points, a survival analysis for interval-censored outcome data in the presence of competing risks will be performed as a supportive analysis, as described in the list of supportive analyses at the end of **Section 7.9.2**.

11. Echocardiographic measurements (i.e., EOA, mean gradient, PVL, LV mass regression, and DVI (severe <0.25, moderate 0.25-0.5, mild >0.5)) at discharge, 30 days, 12 months and annually to 5 years

Echocardiographic measurements will be summarized descriptively based on core lab reported data at each time point within arm. Analysis will be performed using the Implanted analysis set.

EOA and mean gradient will be analyzed as continuous data. Change from baseline in EOA and mean gradient will be summarized descriptively within each arm. Paravalvular leak (PVL) and DVI (severe <0.25, moderate 0.25-0.5, mild >0.5) will be analyzed descriptively as categorical data.

12. Mean gradient ≥ 20 mmHg based on stress echocardiogram at 12 months at select sites

Mean gradient \ge 20 mmHg based on stress echocardiogram at 12 months will be summarized descriptively as categorical data for each treatment arm. Stress echocardiogram will only be

SMART Trial Statistical Analysis Plan	Form
Revision 5.0 Page 25 of 27	Medtronic

performed within a subset of select sites in the trial and analysis will be based on available mean gradient on stress echocardiogram at 12 months. Analysis will use the Implanted analysis set for subjects enrolled in the stress echo sub-study, excluding subjects with LVOT obstruction during exercise.

